4.3. Subject Withdrawal Criteria

A subject may discontinue study drug or withdraw from study participation at any time without bias for any of the following reasons:

Administrative

1. Withdrawal of consent by subject
2. Request of Study Sponsor or Principal Investigator
3. Request of primary care physician
4. Pregnancy (must stop study drug)

NN108 Topiramate as a Disease Modifying Therapy for CSPN

Version 8.0

Version date 8/8/2018

5. Subject deemed lost to follow up/failure to return
6. Early termination of study
7. Other

Adverse Event

1. Worsening of the disease under study
2. Worsening of pre-existing disease (other than disease under study)
3. Intercurrent illness
4. Death
5. Major/clinically significant alteration in laboratory values after beginning study drug
6. Prolonged QTc
7. Active suicidal Ideation based on the C-SSRS
8. Other adverse event

4.4. Study Enrollment Procedures

Subjects will be recruited from 14 NeuroNEXT sites and 1 non-NN site in the United States. Investigators will be responsible for obtaining written consent from each potential subject after adequate explanation of the purpose, study procedures, and any risks associated with the study.

Treatment for each subject will be assigned by a randomized code. A block randomization scheme will be used to ensure approximately even distribution of subjects in treatment groups for each BMI strata.

4.4.1. Subject Recruitment and Retention

Subjects will be recruited from clinics at participating NeuroNEXT Network sites. Postings will be placed on selected website(s). Flyers about the study will be sent to community neurologists at NeuroNEXT clinical sites. Webinars will be conducted for subject recruitment as needed. Interested subjects will be contacted by the investigators or their staff and invited to participate. These recruitment strategies will include a mechanism by which the patients can provide their contact information. We will use the NeuroNEXT Recruitment and Retention Committee to identify recruitment strategies.

4.4.2. Screening Logs

All clinical sites will maintain screening logs documenting demographic information including age, gender, race and ethnicity, reasons for ineligibility at the screening visit, and reasons for non-participation if eligible.

Screening logs to document demographic information and reasons for ineligibility and non-participation will be stored centrally at the NeuroNEXT Data Coordination Center. Information about screening failures and successes will be compiled and reviewed on a periodic basis so that feedback can be provided to sites.

Screening log data will be provided to the study team, de-identified and analyzed to determine the most successful routes for information dissemination and recruitment strategies for ongoing recruitment in this study and for future studies. The study team will work to identify any common reasons for screen failure that might be identified to consider amendments to the study to adjust inclusion/exclusion criteria if a large number of patients are screen failing for specific reasons that would not ultimately affect the study results if allowed. Likewise, reasons for non-enrollment will be tracked centrally. If there are recurring themes adjustments will be attempted to target this problem, as long as the adjustments do not affect the study conduct or data quality.

4.4.3. Informed Consent

Written informed consent will be obtained from each study participant before any study-specific procedures or assessments are done and after the aims, methods, anticipated benefits, and potential hazards are explained. The participant's willingness to participate in the study will be documented in writing in a consent form approved by the NeuroNEXT Central Institutional Review Board (CIRB), which will be signed by the participant with the date of that signature indicated. The investigator will keep the original consent forms and a copy will be given to the participant. It will also be explained to the participant that they are free to refuse entry into the study and free to withdraw from the study at any time without prejudice to future treatment. Written and/or oral information about the study in a language understandable by the participant will be given to all participants.

Informed consent will be obtained by licensed physician investigators only, who are trained on the study and delegated appropriately as being authorized to obtain consent. The site PI will typically be involved in explaining the study and will play a role during the consent process and answering any questions in conjunction with the coordinator, as well as overseeing that the process is carried out correctly.

Optional DNA and tissue banking is planned for future research. Participants will consent to their preference for banking DNA and tissue separately.

4.4.4. Assent

Children (age less than 18) will not be allowed to participate in this study.

4.4.5. Randomization/Treatment Assignment

Randomization to study treatment (either topiramate or matching over-encapsulated placebo) will occur using an interactive web response system (IWRS). Online randomization will follow confirmation of eligibility and completion of all required baseline procedures. Randomization codes will be constructed using random permuted blocks to assure balanced randomization over time with stratification by BMI. BMI of 30.0 will serve as stratification cutoffs reflecting anticipated median values.

Following randomization, subjects will be given a supply of study drug with instructions to take the study drug twice daily using a 2-week dose escalation schedule. Subjects will titrate to two 25mg tablets twice daily, or the maximally tolerated dose.

5. STUDY INTERVENTIONS/ STUDY DRUG

5.1. Study Drug and Dose Selection

The intervention under study is oral topiramate, 100mg daily taken in two divided doses of 50mg. Matching placebo will be identical to topiramate in color, shape, and packaging.

5.2. Dose selection

Previous studies have evaluated topiramate as a potential therapy for pain associated with diabetic neuropathy with mixed results. The dose in these trials varied from 100-400 mg daily^{22,23,64}. The objective of this study is to evaluate the potential efficacy of topiramate as a disease modifying therapy for CSPN associated with metabolic syndrome. Randomized trials in diabetic neuropathy have demonstrated that a dose of 100 mg/day is sufficient to improve both neuropathy associated QOL (as measured by NQOL-DN) and thigh IENFD^{24,25}, while side effects of decreased concentration or fatigue were more common at higher doses. Similarly, a Cochrane review reported no additional benefit to doses over 100 mg daily in topiramate trials for headache⁶⁵. In light of the greater risk of side effects at doses over 100 mg daily, these data support selection of the 100 mg/day target dose.

5.3. Formulation and Packaging

Study drug, or matching placebo, will be provided in labeled packages with sufficient product for study subjects to take four capsules daily for 16 weeks, with sufficient overage in each package to allow for anticipated variation in visit scheduling. Four 132-count bottles will be provided, permitting for 14 days of overage. Each study test article packet will be labeled with the following information:

- Name of Sponsor
- Name and address of study drug distribution center
- Study number and IND number
- Unique drug package number
- Drug treatment label (each kit will list either 25 mg topiramate or placebo)
- Route of administration
- Quantity of dose unit
- Directions for use
- Storage conditions
- Space for investigator name, telephone, dispensing date and subject number
- Space for study subject identifier
- Label statement "Caution: New Drug-Limited by federal law to investigational use"

Label statement “Caution: Keep out of reach of children”

5.3.1. Supplies and Dispensation

Study drug supplies will be received by the site investigator or other authorized study personnel at the study site, managed and stored safely and properly, and kept in a secured location with restricted access. Study staff with responsibility for drug management will keep accurate and complete records of study drug received by the site, dispensed to study subject, and used and returned by study subject.

Study drug will be dispensed by appropriately qualified staff as designated by the investigator’s delegation of authority log. Subjects will self-administer the study drug at home following the instructions provided to the subject at the study visit. The study site investigator will retain returned study drug, or study drug supplies not dispensed to subjects, until the sponsor provides written instructions for disposition.

The study case report forms and source documents will include prompts to record study subject eligibility to receive study drug, study drug dispensed, dosing start date, dosing end date, missing doses, and study drug returned.

5.3.2. Titration Schedule and Dose Adjustments

Subjects randomized to the topiramate arm will start 25mg topiramate once daily in the evening. On day 4 following randomization a morning dose of 25 mg will be added. On day 8 following randomization an additional 25 mg tablet will be added in the evening, and on day 12 a second morning dose will be added so that the subject will be taking a total of 50mg twice daily. Subjects who experience an adverse event during the dose titration may continue at the highest tolerated dose for one week prior to an additional attempt to increase to the targeted dose. Those who are tolerant of a lower dose but intolerant of the target dose will continue on the highest tolerated dose. Results will be analyzed in an intent to treat fashion. If a subject develops a treatment related adverse event, the dose may be lowered at the discretion of the site PI in order to establish a lower maximally tolerated dose. Those who have an adverse event and are unable to continue medication will undergo a termination visit.

In accordance with local regulatory requirements, the investigator, designated site staff, or head of the medical institution (where applicable) must document the amount of investigational product dispensed and/or administered to study subjects, the amount received from the central pharmacy, and the amount destroyed upon completion of the study. An investigator is responsible for ensuring product accountability records are maintained throughout the course of the study. The inventory will include details of *topiramate* received and dispensed to subjects, batch, and ID numbers. All unused *capsules* must be kept until reconciliation of delivery records with accountability logs by the monitor. After the monitor has performed accountability, the site will be instructed by the DCC or designee to either destroy the remaining study drug or return it to the

Central Pharmacy or manufacturer. An accounting must be made of any drug deliberately or accidentally destroyed. Discrepancies between the amount of topiramate received and dispensed drug must be reconciled.

5.4. Concomitant Interventions

The following are permissible as concomitant interventions for neuropathic pain related to CSPN if stable for 8 weeks prior to screening:

- Gabapentin
- Pregabalin
- Tricyclic antidepressants
- Duloxetine
- Venlafaxine
- Tramadol (200mg daily or less)
- Topical lidocaine
- Non-steroidal anti-inflammatory drugs

The intent of the protocol is to keep allowable neuropathic pain agents and dosing unchanged for the duration of the study (8 weeks prior to screening through week 96).

Marijuana, cannabinoids, and alpha lipoic acid (ALA) will be specified as neuropathic pain agents on the concomitant medication form. These products will not require dosing stability, but will be tracked to evaluate any potential impact on outcomes.

If in the opinion of the site investigator, changes in the permissible neuropathic pain agents are required for the safety and/or well-being of the participant between baseline and week 96/ET, the change will be captured in EDC and reported to the PPI. These participants will not be required to discontinue study medication or exit the study.

5.4.1. Prohibited Medications/Interventions

The following medications/interventions are exclusionary:

- Therapeutic anticoagulations including coumadin or oral factor X or thrombin inhibitor therapy
- Topical capsaicin
- Oral prednisone
- Carbonic anhydrase inhibitor (such as acetazolamide)
- Weight loss medications
- Neuropathic pain agents beyond first line agents
- Scheduled opiates, or as needed opiate medications more than three times weekly
- Intrathecal pain pump or spinal cord stimulator
- Current or prior history of topiramate therapy

5.5. Subject Compliance

At each study visit, the site Investigator and/or Study Coordinator will assess the subject's compliance with the study requirements. This will include checks for protocol compliance, including use of study drug in order to assess the reliability of subject-generated data. Subjects who fail to comply with study requirements may be withdrawn from the study.

A serum topiramate level will be measured at baseline and weeks 32, 64, and 96 or ET to assess for compliance or potential crossover (e.g. a participant randomized to placebo taking off study prescription topiramate).

Participants will be asked to hold their morning dose of study medication until after the blood draw at weeks 32, 64, 96/ET. The date and time of last dose of study drug will be recorded. If the participant does not hold the prior dose, the topiramate level should still be obtained. These data will not be shared with the study team until after the study has closed.

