6.13. Early Termination and Premature Withdrawal

Subjects have the right to withdraw from the study at any time without prejudice. The site Investigator may withdraw study drug from a subject in the study in the event of intercurrent illness, adverse events, other reasons concerning the health or well-being of the subject or other administrative reasons. Early termination will be implemented in the case of emergency disclosure of drug treatment (i.e., unblinding). **NOTE: All efforts should be made by study staff to encourage subjects to return for follow-up visit(s). If a subject withdraws consent from the study in writing, no further contact can be made.**

A subject may discontinue study medication for the following reasons:

Administrative

1. Withdrawal of consent
2. Request of Sponsor or Principal Investigator
3. Request of primary care physician
4. Pregnancy
5. Subject deemed lost to follow up/failure to return
6. Termination of study
7. Other

Adverse Event

1. Worsening of the disease under study
2. Worsening of pre-existing disease (other than disease under study)
3. Intercurrent illness
4. Death
5. Major/clinically significant alteration in laboratory values after beginning study drug
6. Suicidality based on the C-SSRS
7. Other adverse event

In the event a participant discontinues study medication for any reason, every effort should be made to complete the evaluation visits at week 32, 64, and 96. An early termination visit should be completed for all participants who are unable or unwilling to complete additional evaluation visits. If a subject is unable to return to the site, or refuses to complete all termination visit procedures, any reasonable study procedures to which the subject consents will be completed.

Should a scheduled in-person visit be impossible, conduct as many of the verbal assessments as possible, with special emphasis on obtaining information on possible AEs, and arrange for return of study drug. Every effort will be made to determine the subject's health status at withdrawal.

Reasons for early termination of the subject prior to completion of the study must be stated in the CRF and in the site source documentation for all study subjects who were enrolled in the study. The CCC and the IMM must be informed within 24 hours of all study subjects who are withdrawn due to an adverse event.

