6.13.4. On Study/Off-Intervention Evaluations

Every possible effort should be made by the site PI to encourage subjects who are no longer taking study drug to remain in the study. They should explain that continued participation will teach us more about the natural history of CSPN progression, the impact of metabolic improvement and weight loss on CSPN, and the clinical relevance of IENFD and other surrogate measures of CSPN progression.

When subjects decide to go off the study drug, it will be a reportable event and the project manager will discuss the reasons for this with site staff to learn the specifics in each case and provide advice on an individual basis about the best ways to keep the subject engaged in the

project. These subjects and their physicians will not be told whether they were given topiramate or placebo.

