7.1.18. Subject Adherence Assessments

At each study visit, the site Investigator and/or Study Coordinator will assess the subject's compliance with the study requirements by performing study drug reconciliation and collecting study drug containers. This will also include reviewing protocol compliance, including use of study drug and concomitant medications. If applicable, subjects who fail to comply with the study requirements may be removed from the study.

The site Investigator and/or Study Coordinator will conduct monthly telephone calls between clinic visits (i.e.: between Baseline and Week 16 calls should occur at Week 4, Week 8, and Week 12) to encourage protocol compliance and enhance retention.

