10. STATISTICAL CONSIDERATIONS

The NeuroNEXT Data Coordinating Center has developed a statistical analysis plan, in collaboration with the protocol principal investigator and protocol steering committee.

a. General considerations. Univariate summaries will be provided for all randomized subjects and by treatment group. Transformations will be considered for continuous variables exhibiting substantial skewness. Analyses of topiramate's effect will be conducted according to randomized treatment assignment in accordance with the intent-to-treat principle.

b. Strategy for evaluating the Co-Primary Endpoints in Aim 1. Analyses of the effects of topiramate on the co-primary endpoints will be interpreted from two perspectives. From a scientific investigational perspective, IENFD and NQOL-DN will be viewed as representing separate outcome domains, and the hypotheses of treatment effects on these outcomes will be considered conceptually distinct. Because positive findings from this early-phase trial will be subjected to confirmation in a subsequent pivotal trial, the scientific hypotheses of treatment effects on the conceptually distinct co-primary endpoints will be tested on a comparison-wise basis without multiple comparison adjustment in order to enhance statistical power^{74,75}. From a decision-

theoretic perspective, the results of this early-phase clinical trial will be applied to determine whether to proceed to a larger pivotal trial with a definitive clinical endpoint. Proceeding to a full-scale trial will be deemed appropriate if the present trial demonstrates that topiramate has a benefit based on either IENFD or NQOL-DN and does not have an adverse effect the other outcome. Because this choice represents a single decision point, a single global decision rule to control the risk of inappropriately proceeding to a full-scale trial will be applied. The analyses of the effect of topiramate on the IENFD and NQOL-DN as distinct endpoints are described first, followed by a global strategy for deciding whether to proceed to a full-scale trial.

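### Sections 5.5, 7.1.18 and 6.13 allow outcome follow-up to end for non-compliance or unblinding, in conflict with the plan's own aim of following participants off drug to week 96

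*Combined protocol and SAP*

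**What the plan says.** Four provisions allow or suggest an end to follow-up:

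- Section 5.5: "Subjects who fail to comply with study requirements may be withdrawn from the study".
- Section 7.1.18, after describing drug reconciliation, container collection and review of concomitant medications: "subjects who fail to comply with the study requirements may be removed from the study". The sentence is qualified as applying where applicable.
- Section 6.13: "Early termination will be implemented in the case of emergency disclosure of drug treatment (i.e., unblinding").
- Section 5.3.2: "Those who have an adverse event and are unable to continue medication will undergo a termination visit".

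Section 4.3 gives one list of reasons that serves both for stopping drug and for leaving the study. It includes a request by the sponsor or principal investigator and an open category for other reasons.

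Other provisions point the opposite way. For a participant who stops medication for any reason, 6.13 says "every effort should be made to complete the evaluation visits at week 32, 64, and 96". It adds: "An early termination visit should be completed for all participants who are unable or unwilling to complete additional evaluation visits". Section 6.13.4 tells sites to "encourage subjects who are no longer taking study drug to remain in the study". Section 10.a says analyses will be "conducted according to randomized treatment assignment in accordance with the intent-to-treat principle".

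The early termination visit (6.12) includes both co-primary measures, the distal thigh biopsy and the NQOL-DN. Section 10.d relies on restricted maximum likelihood under missing at random, with multiple imputation using auxiliary variables as the sensitivity analysis.

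**The concern.** The plan treats two similar participants differently. One who formally stops study drug is to be evaluated at weeks 32, 64 and 96. One who keeps taking it irregularly may be removed from the study altogether, at the site's discretion and with no threshold. Section 5.5 links the compliance check to how far participant-supplied data can be trusted. That does not justify ending collection of IENFD, which is measured in a central laboratory.

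At stake are the scheduled values after removal, including week 96. Poor compliance and emergency unblinding can both be related to tolerability, and so to the assigned arm and to later outcome. If removal depends on things not captured in the observed data, the primary mixed model and the imputation analysis share the same weakness, because both assume missing at random. No analysis under a missing-not-at-random assumption is named. The Go/No-Go rule in 10.f compares point estimates with fixed cut-offs, so a shift in an estimate moves the decision directly.

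**Working it through.** **Step 1. The provisions side by side.**

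| Situation | Study follow-up according to the text |
|---|---|
| Stops drug for any reason | Continue weeks 32, 64, 96 (6.13); encourage to stay (6.13.4) |
| Stops drug for an adverse event | Termination visit (5.3.2), but also the row above |
| Does not comply | May be removed from the study (5.5, 7.1.18) |
| Emergency unblinding | Early termination, of drug or study not stated (6.13) |

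Rows 1 and 2 conflict. Row 3 ends follow-up for a lesser departure than row 1. Row 4 is ambiguous. The early termination visit is specified for participants who cannot or will not return, so a participant removed by the site is not expressly covered.

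**Step 2. The plan's own power figure.** Inputs from 10.e: SD of NQOL-DN change 16.4, correlation 0.60, difference 7.9, 125 randomized, 12% loss. Equal allocation is assumed, giving 110/2 = 55 per arm.

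- Residual SD = 16.4 × √((1 + 0.60)/2) = 14.67.
- SE = 14.67 × √(2/55) = 2.80.
- Power = 80.6% (normal approximation) or 79.9% (t), against 80% stated.

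The figure reproduces and already allows for 12% loss, so there is no arithmetic error here. If removals came on top of that, power would be 79.3% at 15% total loss and 76.8% at 20%. The IENFD power cannot be rebuilt, because its variance components are not given.

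**Step 3. IENFD, illustrative.** Assume a fraction p of the topiramate arm is removed before week 32, has no exit biopsy, and would have followed the placebo slope. With d the slope difference among those who remain:

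- Intent-to-treat difference = (1-p)·d + p·0 = (1-p)·d.
- Estimated difference = d, so the inflation factor is 1/(1-p).

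Section 3 projects 125 at baseline and 120 at week 32, a loss of 5 (4%). With 125/2 = 62.5 per arm, all 5 in the topiramate arm is 5/62.5 = 8%.

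| p | Inflation | Intent-to-treat value when 0.30 is estimated | When 0.47 is estimated |
|---|---|---|---|
| 4% | 1/0.96 = 1.04 | 0.288 | 0.451 |
| 8% | 1/0.92 = 1.09 | 0.276 | 0.432 |
| 10% | 1/0.90 = 1.11 | 0.270 | 0.423 |
| 20% | 1/0.80 = 1.25 | 0.240 | 0.376 |

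Units are fibers/mm/year; 0.30 is the Go cut-off and 0.47 the powered difference. The inflation is multiplicative, so this mechanism leaves a true zero difference at zero.

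**Step 4. NQOL-DN, illustrative.** Assume a fraction f of the topiramate arm is removed, with unobserved week 96 scores worse than those retained by D points in a way the observed data do not explain. Bias toward topiramate = f × D. With SE 2.80:

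| f | D | Bias (points) | Share of 7.9 | Two-sided type I error |
|---|---|---|---|---|
| 5% | 8 | 0.40 | 5% | 5.2% |
| 8% | 12 | 0.96 | 12% | 6.4% |
| 12% | 16.4 | 1.97 | 25% | 10.8% |

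All values of p, f and D are assumptions. The documents give no expected removal rate.

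**The case against.** The other side has real force. Removal is permitted, not required. The early termination visit obtains both co-primaries at exit, so some of the course is observed if that visit takes place. The side effects most likely to disturb dosing are managed within the protocol: 5.3.2 and Section 8 allow a lower tolerated dose, and 6.13.2 provides for restarting. A participant on fewer capsules for that reason is compliant. Compliance in 5.5 and 7.1.18 covers study requirements generally, not capsules alone. Sites are blinded and do not see topiramate levels. Missing-at-random methods handle removal that depends only on observed data.

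This defeats several stronger readings:

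- A reader might infer that outcome data will be lost selectively, mainly from the topiramate arm. The documents support only that they can be.
- A reader might infer that unblinding ends study participation. Elsewhere 6.13 and 6.14 do use early termination in that sense. But the unblinding sentence directly follows one about withdrawing drug and precedes a note urging return for follow-up, so it is ambiguous.
- A reader might infer that 10.a is breached. It governs analysis by assigned arm, which removal does not change. What suffers is the completeness of the data that such an analysis needs.

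The conflict itself survives. An exit measurement is not a week 96 measurement. The IENFD model is indexed to baseline and three scheduled visits with an unstructured covariance, and does not say how an off-schedule exit biopsy enters. Auxiliary variables such as capsule counts help only if similar non-compliers stay in to inform the imputation.

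**Conclusion.** The point holds as an internal conflict with a possible bias, not as a demonstrated one. Sections 5.5 and 7.1.18 allow open-ended discretion to end outcome follow-up, the unblinding sentence in 6.13 leaves its scope unstated, and both sit against 6.13 and 6.13.4. This weakens the intent-to-treat aim and adds avoidable missingness to an analysis that rests on missing at random.

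On the plan's own projected losses, the IENFD slope difference would be inflated by about 4% (p = 4%) to 9% (p = 8%). This assumes removal before week 32, no exit biopsy, a placebo-like course and equal allocation; the 9% also needs every projected early loss to be in the topiramate arm. A reader might reach for 20% removal, which makes a true 0.24 appear as the Go cut-off of 0.30. That is an extreme case. Removing 10% to 20% of one arm means about 6 to 13 participants (62.5 × 0.10 = 6.25; 62.5 × 0.20 = 12.5) before week 32, against 5 projected from all causes in both arms. The projection is not a ceiling, but nothing in the documents supports such rates. For the NQOL-DN the bias is likewise small unless removals are numerous, one-sided and strongly prognostic. The change is worth making because it is cheap and removes the question.

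**What to change.** 1. In 5.5 and 7.1.18, replace the withdrawal and removal sentences with a statement that non-compliance is recorded and counselled and does not by itself end outcome follow-up.
2. In 6.13, state that emergency unblinding is documented and flagged, and does not by itself end the biopsy, NQOL-DN and safety evaluations through week 96.
3. Reconcile 4.3 and the termination-visit sentence in 5.3.2 with 6.13 and 6.13.4 on whether outcome follow-up continues. In 4.3, separate reasons for stopping drug from reasons for leaving the study. Without this, removal at an investigator's request remains available and the conflict persists.

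Handling of study drug in each case is for the sponsor; the change concerns data collection only.

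The cost is a few reworded sentences in an amendment, and the visits are already in the schedule. The small downside is that a few NQOL-DN scores will be collected after participants know their arm. These can be flagged.
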